8.1. Adverse Events (AE) and Serious Adverse Events (SAEs)

The definitions of an AE or SAE can be found in [Appendix 2](#).

The investigator and their designees are responsible for detecting, documenting and reporting events that meet the definition of an AE or SAE.

8.1.1. Time period and Frequency for collecting AE and SAE information

- AEs and SAEs will be collected from the start of informed consent until the follow-up contact, at the time points specified in the Time and Events Table (Section 7.1).
- AEs and SAEs collected before the start of study treatment will be recorded as pre-treatment AEs/SAEs.
- Any SAEs assessed as related to study participation (e.g., protocol-mandated procedures, invasive tests, or change in existing therapy) or related to a GSK product will be recorded from the time a subject consents to participate in the study up to and including any follow-up contact.
 - All SAEs will be recorded and reported to the sponsor or designee immediately and under no circumstances should this exceed 24 hours, as indicated in [Appendix 2](#). The investigator will submit any updated SAE data to the sponsor within 24 hours of it being available.
- Investigators are not obligated to actively seek AEs or SAEs in former study subjects. However, if the investigator learns of any SAE, including a death, at any time after a subject has been discharged from the study, and he/she considers the event reasonably related to the study treatment or study participation, the investigator must promptly notify GSK.

NOTE: The method of recording, evaluating and assessing causality of AEs and SAEs plus procedures for completing and transmitting SAE reports to GSK are provided in [Appendix 2](#).

8.1.2. Method of Detecting AEs and SAEs

Care will be taken not to introduce bias when detecting AEs and/or SAEs. Open-ended and non-leading verbal questioning of the subject is the preferred method to inquire about AE occurrence. Appropriate questions include:

- “How are you feeling?”
- “Have you had any (other) medical problems since your last visit/contact?”

- “Have you taken any new medicines, other than those provided in this study, since your last visit/contact?”

8.1.3. Follow-up of AEs and SAEs

After the initial AE/SAE report, the investigator is required to proactively follow each subject at subsequent visits/contacts. All SAEs, and non-serious AEs of special interest will be followed until resolution, until the condition stabilizes, until the event is otherwise explained, or until the subject is lost to follow-up. Further information on follow-up procedures is given in [Appendix 2](#).

8.1.4. Regulatory Reporting Requirements for SAEs

Prompt notification by the investigator to GSK of SAEs and non-serious AEs related to study treatment (even for non- interventional post-marketing studies) is essential so that legal obligations and ethical responsibilities towards the safety of subjects and the safety of a product under clinical investigation are met.

GSK has a legal responsibility to notify both the local regulatory authority and other regulatory agencies about the safety of a product under clinical investigation. GSK will comply with country specific regulatory requirements relating to safety reporting to the regulatory authority, IEC and investigators.

Investigator safety reports are prepared for suspected unexpected serious adverse reactions according to local regulatory requirements and GSK policy and are forwarded to investigators as necessary.

An investigator who receives an investigator safety report describing a SAE(s) or other specific safety information (e.g., summary or listing of SAEs) from GSK will file it with the IB and will notify the IEC, if appropriate according to local requirements.

9. DATA MANAGEMENT

- For this study data will be double-entered into a clinical database management system (ClinPlus Version 3.3).
- Management of clinical data will be performed in accordance with applicable GSK standards and data cleaning procedures to ensure the integrity of the data, e.g., removing errors and inconsistencies in the data.
- Adverse events and concomitant medications terms will be coded using Medical Dictionary for Regulatory Activities (MedDRA) and an internal validated medication dictionary, GSKDrug by GSK.

Original CRFs will be retained by GSK, while the investigator will retain a copy. Subject initials will not be collected or transmitted to GSK according to GSK policy.

10. DATA ANALYSIS AND STATISTICAL CONSIDERATIONS

10.1. Hypothesis and Treatment Comparisons

Given this is the first time in human trial for GSK3036656, no formal statistical hypotheses are to be tested. Where appropriate, an estimation approach will be taken, and point estimates and confidence intervals (CIs) will be constructed.

10.2. Sample Size Considerations

The planned sample size is 18 subjects for Part A of this study (9 subjects per cohort) and up to 40 subjects for Part B (10 subjects per cohort). Additional subjects may be recruited as replacement for withdrawn subjects.

No statistical techniques were used to calculate the sample size, and because this is a FTIH study, no information on PK variability is available to allow any precision estimate.

10.2.1. Sample Size Re-estimation

No sample size re-estimation is currently planned for this study.

10.3. Data analysis Considerations

Statistical analyses will be performed by, or under the direct auspices of, Statistics, Programming and Data Sciences (SPDS), GlaxoSmithKline.

Complete details of the planned statistical analyses will be provided in the RAP.

10.3.1. Interim Analysis

No formal interim analyses are planned for this study. However, safety, tolerability, and pharmacokinetic data will be reviewed before each dose escalation in Part A (single dose) and Part B (repeat dose), and prior to the investigation of the food effect.

The relationship between dose and plasma GSK3036656 exposure, and associated variability will be characterized by a power model once data are available from 3 dose levels. Prior to that, prediction of the human exposure at the next dose will be based on population PK modelling (if feasible) or on the assumption of dose–exposure proportionality (i.e., doubling the dose gives an approximate doubling of exposure). If prior PK results show less than proportional increase in exposure with increasing dose, the prediction will be based on the assumption that the fold exposure increase to fold dose increase ratio will be the same with the current dose escalation as it was with the previous one. If prior PK results show more than proportional increase in exposure with dose, subsequent dose escalations will not be higher than 3-fold. The power model will be updated as data become available throughout the study. During dose escalation, and once data is available from 3 doses, a Bayesian predictive probability that an individual will have $AUC(0-24)$ greater than 4.9 $\mu\text{g.h/mL}$ or a C_{max} greater than 0.443 $\mu\text{g/mL}$,

will be calculated for the next dose level and used together with safety and tolerability data to aid the next dose selection.

The Bayesian predictive probability will be based on Whitehead's model [[Whitehead, 2001](#)]:

$$\log(y_{ij}) = \theta_1 + \theta_2 \cdot \log(d_{ij}) + \varepsilon_{ij}$$

where

- y_{ij} is the observed or predicted log-AUC variable (AUC[0-24]) or log-Cmax of the j-th dose d_{ij} administered to the i-th subject
- θ_1, θ_2 are population intercept and slope, respectively.
- ε_{ij} is a random error term, with mean zero and variance σ^2 .

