smaller doses will be made by the GSK study team in conjunction with the Principal Investigator. Post-dose, subjects will undergo safety and PK assessments. All subjects will remain in the unit until the 72 hour PK sample has been taken since this will enable a better assessment of their safety and will reduce the risk of subjects not returning for their visits. Subjects will be released at the discretion of the investigator following completion of the assessments provided there are no safety concerns identified from review of the clinical safety data. Approximately 14 days after their last dose, subjects will return to the unit for a follow-up visit.

The starting dose in Part A will be 5 mg. The dose will then be escalated up to a dose (no higher than 1500 mg) at which PK exposures do not exceed predefined limits determined from preclinical safety data (individual AUC[0-24] <4.9 µg.h/ml, individual Cmax <0.443 µg/ml). Dose escalation will only take place provided GSK3036656 is well tolerated and following review of all available safety, tolerability and pharmacokinetic data from the previous treatment (dosing) period by the Dose Escalation Committee (Section 6.3).

[figure not shown]
The two cohorts in Part A will be dosed sequentially (i.e., dosing in Cohort 2 starts after dosing in Cohort 1 is completed). If it is considered desirable to dose Cohorts 1 and 2 in an overlapping/interlocking fashion (for example, if the half-life of GSK3036656/washout period makes sequential dosing impractical), approval for such dosing will be sought from the Regulatory Agency. Dosing in an overlapping/interlocking fashion will only take place if such approval is obtained. In any case, a washout period of at least 4 half-lives will be required before the same group of subjects is dosed again.

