5.5. Dose Escalation Stopping Criteria

Dose escalation in Part A or Part B will be stopped if any of the following occurs in a group/cohort:

1. There is substantially increased incidence and/or severity of clinically significant adverse events or withdrawals possibly related to GSK3036656 in the active treatment subgroup at the last dose level administered as compared to the placebo subgroup. The GSK Study Team in conjunction with the study investigator will determine the significance of the adverse events or withdrawals and make a decision about whether stopping further dose escalation is necessary.
2. At least one subject has a plasma AUC (0-24) higher than 4.9 µg.h/mL or a plasma Cmax higher than 0.443 µg/mL on any day.
3. For Part A, no meaningful increase in exposure is observed with increase in dose (i.e., a plateau in exposures is reached).

Note: If dose escalation is stopped due to reasons 1 or 2 above occurring at the last dose, dosing at a lower level (e.g., an intermediate level between the last dose and a previous dose where dose escalation stopping criteria were not met) could be allowed. The GSK Study Team in conjunction with the study investigator will decide whether dosing at such level could be done and will select the dose to be administered.

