6.3. Planned Dose Escalation and Adjustments

After the initial dose of GSK3036656, the decision to proceed to each subsequent dose level will be made by the Dose Escalation Committee (DEC) based on safety, tolerability and preliminary pharmacokinetic data from the prior lower dose level (Further details regarding dose escalation can be found in the 201040 Dose Escalation Charter). In Part A, safety data for at least 5 days post-dose and PK data for at least 2 days (48 hours) postdose from at least 4 subjects who received active treatment at the prior lower dose level will be reviewed before dose escalation. In Part B, safety data for at least the first 1 week (7 days) of dosing and PK data for at least the first 2 days (48 hours) of dosing from at least 4 subjects who received active treatment at the prior lower dose level will be reviewed before dose escalation. The actual doses to be administered will be selected by the DEC and may involve either an increase or a decrease in the dose, or repeating the same dose.

The exposures (AUC, Cmax) expected with the next selected dose will be predicted by pharmacokinetic assessment and modelling, and by calculating Bayesian predictive probabilities as data permit (more details in Section 10.3.1).

In toxicology studies in dogs, heart valvular and vascular lesions have been observed at relatively high doses and exposures; no such lesions have been seen in rats at similar exposures. To avoid the risk of this adverse event in the FTIH subjects, exposures in the FTIH study will be limited to predefined levels. Based on discussions with the GSK Cardiovascular Safety panel, the study will aim to limit the maximum individual daily plasma AUC(0-24) and Cmax after single or repeat dose to 4.9 µg.h/mL and 0.443 µg/ml, respectively - a 30-fold margin from the corresponding dog NOAEL exposures of 147.0 µg.h/mL and 13.3 µg/ml at which no valvular or vascular lesions have been detected.

Note: The term “mean” applied to group human exposure parameters (e.g., AUC) in this section refers to Geometric Mean of a dose cohort.

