6.3.1. Dose escalation in Part A

In Part A, bigger dose escalation steps may be allowed at lower doses and systemic exposures as the expected risk of adverse events at these exposures is low. At higher doses, smaller dose escalation steps will be used to minimize the risk of adverse events and gastrointestinal intolerance.

The following rules will guide dose selection in Part A:

1. No dose escalation to the next dose will be higher than 6-fold.
2. Once the dose is ≥ 300 mg, any further dose escalation will be no higher than 3-fold irrespective of the observed exposures.
3. The highest dose in Part A will not exceed 1500 mg.
4. A proposed dose will be acceptable if the predicted probability of an individual exceeding a Day 1 plasma AUC (0-24) of 4.9 µg.h/mL or Cmax of 0.443 µg/mL, as estimated by PK modeling and Bayesian analysis (if feasible), is no more than 10%.

5. Based on prior PK data, individual doses may be adjusted, if needed, such that a predicted individual Day 1 AUC (0-24) or Cmax does not exceed 4.9 $\mu\text{g.h/mL}$ or 0.443 $\mu\text{g/mL}$, respectively.

Dosing with food in Part A will be initiated after the exposures achieved with at least two dose levels administered in a fasted state are already known.

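### SAP 7.1.3 pairs an OFV drop of 3.32 with 0.05, which is not the chi-square cut-off; separately, the early fallback exposure prediction needs a formula

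*Protocol*

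**What the plan says.** **Model selection.** SAP 7.1.3 plans a fit-for-purpose population PK model. Candidates are chosen mainly on an OFV reduction of at least 3.32, labelled as chi-square below 0.05, together with better diagnostic plots. A visual predictive check follows. No degrees of freedom are given.

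**Fallback prediction.** Under protocol 10.3.1 the dose-exposure relationship is "characterized by a power model once data are available from 3 dose levels". Until then, population PK is used if feasible, and otherwise dose proportionality. If exposure has risen less than proportionally, the prediction rests on this premise: "fold exposure increase to fold dose increase ratio will be the same with the current dose escalation as it was with the previous one". SAP 7.1.3 repeats that sentence. Neither document adds an equation or an example.

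**Use.** Protocol 6.3 relies on such predictions: "The exposures (AUC, Cmax) expected with the next selected dose will be predicted by pharmacokinetic assessment and modelling". It refers to a Dose Escalation Charter for further detail. That charter is not among the documents supplied.

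**The concern.** The 3.32 threshold is the SAP's only numerical criterion for choosing the model that is the first-choice route to early exposure predictions. If the number and its significance level disagree, an analyst cannot tell which of the two governs.

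The fallback sentence can be turned into arithmetic in more than one way. The most literal version gives a result that cannot be right if exposure rises with dose: a predicted fall at a higher dose. Two analysts following the same sentence could also bring different predictions to the Dose Escalation Committee.

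**Working it through.** **1. OFV cut-off.** The inputs are 3.32 and 0.05 (SAP 7.1.3). The df are an assumption, so a range is shown.

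| Reference distribution | 0.05 cut-off | p for 3.32 |
|---|---|---|
| Chi-square, 1 df | 3.84 | 0.068 |
| Chi-square, 2 df | 5.99 | 0.190 |
| Boundary mixture, 0/1 df (one variance component) | 2.71 | 0.034 |
| Boundary mixture, 1/2 df | 5.14 | 0.129 |

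The plan's pairing of 3.32 with 0.05 is not reproduced in any row.

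**2. Fallback, read literally.** Let F1 and E1 be the previous fold dose and fold exposure, and F2 the next fold dose. Holding the ratio fixed gives a predicted fold exposure of (E1/F1) × F2.

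- As F2 approaches 1, the prediction tends to E1/F1 instead of 1: 0.83 after 6×/5×, 0.67 after 6×/4×, 0.50 after 6×/3×.
- A fall is predicted when F2 < F1/E1, that is, below 1.2, 1.5 and 2.0 in those three cases.

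Neither result depends on a comparison model.

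**3. Against two other formulas.** The incremental form is 1 + (E1−1)/(F1−1) × (F2−1). The log-log form is F2^b with b = ln E1/ln F1, which is the power model through the same two points. The E1 and F1 values are illustrative. They respect the protocol 6.3.1 cap: "No dose escalation to the next dose will be higher than 6-fold".

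| Previous step, then next | Literal | Incremental | Log-log |
|---|---|---|---|
| 6×/5×, then 2× | 1.67 | 1.80 | 1.86 |
| 6×/4×, then 2× | 1.33 | 1.60 | 1.71 |
| 6×/4×, then 1.5× | 1.00 | 1.30 | 1.37 |
| 6×/3×, then 1.5× | 0.75 | 1.20 | 1.28 |
| 3×/2×, then 6× | 4.00 | 3.50 | 3.10 |

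Literal divided by log-log equals (F2/F1)^(1−b). With b < 1 the literal form is therefore lower for a smaller next step, identical for equal steps, and higher for a larger one.

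**4. If exposure saturates.** Take y = d/(d+K) with K = 9 times the first dose. This reproduces 6×/4×: (6/15)/(1/10) = 4. True folds at the next 1.5-, 2- and 3-fold steps are 1.25, 1.43 and 1.67. Prediction errors are:

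| Form | 1.5-fold | 2-fold | 3-fold |
|---|---|---|---|
| Literal | −20% | −7% | +20% |
| Incremental | +4% | +12% | +32% |
| Log-log | +9% | +20% | +40% |

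**5. Where the fallback can act.** Protocol 4.1 says: "The starting dose in Part A will be 5 mg". With the 6-fold cap the second level is at most 5 × 6 = 30 mg and the third at most 30 × 6 = 180 mg. In Part A the rule therefore bears mainly on the prediction for the third level, made from 30 mg or less.

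**The case against.** **On the OFV.** For a single variance component tested on its boundary, 3.32 does satisfy p < 0.05, and the SAP does model inter-individual variability. Diagnostic plots and a predictive check also enter the choice. This stands: a reader might infer that 3.32 always fails the 0.05 level, and that goes too far. But the SAP does not limit the criterion to that case, and the cut-off there would be 2.71.

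**On the fallback.** Population PK comes first, and sampling is rich (17 time points per subject in Part A). Committee review, sentinel dosing and individual dose adjustment (protocol 6.3.1, rule 5) remain. So does the protocol 5.5 stop: "At least one subject has a plasma AUC (0-24) higher than 4.9" (µg.h/mL). The charter may hold a formula. All of this stands and keeps the point small.

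Three stronger readings are tempting, and the documents do not support them:

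- *Under-prediction is the expected case.* Protocol 6.3.1 does say: "At higher doses, smaller dose escalation steps will be used to minimize the risk of adverse events". But it also allows bigger steps at lower doses, and its only numerical marker for tighter steps is 300 mg. The affected step starts at 30 mg or less.
- *The fallback lets doses through the 10% exceedance criterion.* No passage ties this point prediction to that criterion. An illustration (current geometric mean 2.0, lognormal with 30% CV, both assumed; 2-fold step on the saturating curve) gives a true exceedance of 3.3%, against 1.9% literal, 7.3% incremental and 11% log-log. There the literal form errs low but does not change the answer, whereas the log-log form would reject an acceptable dose.
- *The fallback contradicts the power model, which should replace it.* The two apply in sequence. On the saturating curve the literal ratio is closer than the log-log form at 2- and 3-fold.

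**Conclusion.** Two points hold.

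First, 3.32 is not the 0.05 cut-off under any of the reference distributions examined. On the usual 1-df test, which is an assumption, the nominal level is 6.8% instead of 5%. No effect on any exposure prediction is shown. It is an error in a stated threshold that one number corrects.

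Second, and minor, the fallback is given in words only in the two documents supplied. Its literal reading does not return the observed exposure when the step shrinks to nothing, and it predicts a fall when F2 < F1/E1. With equal steps it agrees with the power model. It matters only if population PK is infeasible, the first step was less than proportional and fewer than three levels exist, so it affects essentially one Part A prediction. The size of any error depends on the shape of the true dose-exposure curve, which is unknown. The documents do not show that a wrong dose would be accepted.

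**What to change.** **SAP 7.1.3, OFV.** Change the cut-off to 3.84 for one added parameter and state the df. Alternatively, keep 3.32 and give its p-value as about 0.07 (1 df).

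**Protocol 10.3.1 and SAP 7.1.3, fallback.** State a formula, applied to AUC(0-24) and Cmax separately, that gives a fold of 1 at an unchanged dose and cannot predict a fall. Either form in step 3 of the working would do, with its coefficient, (E1−1)/(F1−1) or ln E1/ln F1, not below 0. The log-log form matches the power model that follows. Its price is the larger over-prediction if exposure saturates: about 20% at 2-fold and 40% at 3-fold in the 6×/4× example, against 12% and 32% for the incremental form. That errs on the cautious side but could turn down an acceptable dose, so the choice is the sponsor's. If the charter already holds a formula, cite it and check that it meets the two conditions.

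The cost is one sentence in each document and one number in the SAP. No dose, step cap or exposure limit changes.

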7.1.3. Overview of Planned PK Dose Escalation Analyses

Dose escalation for the first 2 dose levels will be based on population PK modelling (if feasible) or on the assumption of dose–exposure proportionality (i.e., doubling the dose gives an approximate doubling of exposure). If prior PK results show less than proportional increase in exposure with increasing dose, the prediction will be based on the assumption that the fold exposure increase to fold dose increase ratio will be the same with the current dose escalation as it was with the previous one. If prior PK results show more than proportional increase in exposure with dose, subsequent dose escalations will not be higher than 3-fold.

The population PK model will be a fit for purpose model. Candidate model selection will be primarily based on a significant reduction in the objective function value (≥ 3.32 , $\chi^2 < 0.05$) and improvement in the fits of diagnostic scatter plots. Inter-individual variability will be modelled using an exponential error model and residual error will be described by a proportional, proportional plus additive, or additive error model, depending on the data. Model performance will be evaluated using a visual predictive check. Simulations for dose recommendations will be conducted to determine the probability of an individual subject exceeding the defined exposure margins for AUC and Cmax.

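### Before three dose levels are available, the fallback exposure forecast has no rule for a more-than-proportional rise, only a 3-fold step cap

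*Protocol*

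**What the plan says.** Protocol 10.3.1 starts a power model once three dose levels have data. Until then SAP 7.1.3 reads: "Dose escalation for the first 2 dose levels will be based on population PK modelling (if feasible) or on the assumption of" dose proportionality. Protocol 10.3.1 has the same hierarchy. Both documents then split by what the earlier step showed:

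- Less than proportional: "the prediction will be based on the assumption that the fold exposure increase to fold dose increase ratio will be the same" as at the previous escalation. This is a forecast rule.
- More than proportional: "If prior PK results show more than proportional increase in exposure with dose, subsequent dose escalations will not be higher than 3-fold". This limits the step and says nothing about the forecast.

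The controls around the forecast are these:

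- Protocol 6.3.1 rule 1: "No dose escalation to the next dose will be higher than 6-fold".
- Protocol 6.3.1 rule 4 accepts a dose only if the predicted probability that an individual exceeds AUC(0-24) 4.9 µg.h/mL or Cmax 0.443 µg/mL is at most 10%.
- Protocol 6.3.1 rule 5: "Based on prior PK data, individual doses may be adjusted, if needed, such that a predicted individual Day 1 AUC (0-24) or Cmax" stays within those limits.
- Protocol 6.3 requires review of PK data "from at least 4 subjects who received active treatment at the prior lower dose level". It refers to 10.3.1 for the prediction method and to a separate Dose Escalation Charter for further detail on escalation.
- Protocol 5.5 stops escalation if "At least one subject has a plasma AUC (0-24) higher than 4.9" µg.h/mL, or has a Cmax above 0.443 µg/mL.

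**The concern.** Non-proportionality seen in the data changes the forecast when that lowers it, but not when it would raise it. In the second case the only fallback in the text is a slope of 1, which the data have just contradicted. The error then runs in the unsafe direction. The exposure limits exist because of heart valve and vascular lesions in dogs, which Protocol 4.6.1 describes as impossible to monitor in humans. Rules 4 and 5 both work from predicted exposure, so a low forecast weakens both.

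**Working it through.** **1. The plan's own figures.** The limits reproduce: 147.0/30 = 4.9 and 13.3/30 = 0.443. Protocol 4.5 states a chance below 1% that an individual exceeds the AUC limit at 5 mg. Take lognormal clearance with the sponsor's 50% CV, so log SD s = √ln(1.25) = 0.472, a body weight of 70 kg (315 L ÷ 4.5 L/kg), and AUC = F × dose/CL. The lowest predicted clearance, 1.1 mL/min/kg, is 4.62 L/h. With F = 1, AUC is 5/4.62 = 1.08 µg.h/mL and the exceedance probability is 0.07%. With F = 1.1 and the clearance read as an arithmetic mean it is 0.29%. Both agree with the stated figure, so the same variability is used below.

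**2. Which decision is affected.** Dose 2 has no earlier step from which to judge proportionality. After dose 3 the power model takes over. That leaves the choice of dose 3 in Part A. Part B is less exposed, because Protocol 6.3.2 also bases its forecasts on Part A PK.

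**3. Size of the shortfall.** Let exposure rise as dose^b. The documents give no b, so 1.2 to 1.5 is an assumption. For a step of f-fold, the true rise is f^b and the proportional forecast is f, so true/forecast = f^(b−1).

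| b | f = 2 | f = 3 | True rise at f = 3 |
|---|---|---|---|
| 1.2 | 1.15 | 1.25 | 3.74 |
| 1.3 | 1.23 | 1.39 | 4.17 |
| 1.5 | 1.41 | 1.73 | 5.20 |

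The cap does bound the error. The true rise at 3-fold stays below 6-fold until b = ln 6/ln 3 = 1.63.

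**4. Effect at the 10% gate.** With s = 0.472 for exposure, a forecast geometric mean meets rule 4 only up to 4.9/exp(1.2816 × 0.472) = 2.68 µg.h/mL, or 0.242 µg/mL for Cmax. If dose 3 is placed exactly there by a proportional forecast, the true exceedance is 1 − Φ(1.2816 − ln(3^(b−1))/s):

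- b = 1.2: 1 − Φ(1.2816 − 0.465) = 20.7%
- b = 1.3: 1 − Φ(1.2816 − 0.698) = 28.0%
- b = 1.5: 1 − Φ(1.2816 − 1.163) = 45.3%

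At an assumed 30% CV the figures are 29.7%, 43.7% and 72.2%.

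**5. Can dose 3 be near the gate?** The highest dose 3 in this branch is 5 × 6 × 3 = 90 mg. Use a one-compartment model with instant absorption, 70 kg, CL 4.62 to 30.2 L/h, V 245 to 315 L and F 0.6 to 1. Then AUC(0-24) = (F × dose/CL)(1 − exp(−24 CL/V)) runs from 1.61 to 7.09 µg.h/mL, and Cmax = F × dose/V from 0.171 to 0.367 µg/mL. The gate values of 2.68 and 0.242 lie inside these ranges, so the gate could decide dose 3.

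**6. The fold-ratio rule.** After a first step F1, it forecasts f × F1^(b−1) against a true f^b. For b below 1 this is too low whenever f is smaller than F1:

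- 6-fold then 3-fold, b = 0.8: 2.10 against 2.41.
- 6-fold then 3-fold, b = 0.5: 1.22 against 1.73.
- 6-fold then 1.5-fold, b = 0.5: 1.5 × 6^(−0.5) = 0.61, a predicted fall in exposure after a dose increase, against a true 1.22.

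It is too high when the next step is the larger one (2-fold then 3-fold, b = 0.8: 2.61 against 2.41).

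**The case against.** **The conditions are narrow.** Population PK must be infeasible, the first step must show a more-than-proportional rise, the trend must continue, and dose 3 must be near the gate. Each profile has 17 plasma samples and six subjects per dose receive active drug, so about 12 rich profiles are planned before dose 3. SAP 7.1.3 also describes the population model and simulations of individual exceedance. This stands. It limits the priority, but it does not supply the missing rule.

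**The text may not be the whole rule.** No sentence tells the committee to keep a proportional forecast once the data contradict it, and the Charter may say more. This stands too. The claim is about what the protocol and SAP state.

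**A cap is a defensible answer to a noisy two-point slope.** It halves the permitted step, and committee review and the stop rule remain. That limits the harm. But the stop rule acts only after a volunteer has exceeded a limit, and none of these measures corrects the number that rules 4 and 5 use.

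**A stronger reading does not hold.** At a 3-fold step, a forecast between 3.93, 3.52 or 2.83 and 4.9 µg.h/mL (from 4.9/3^(b−1)) would look acceptable while the true value is above the limit. A reader might infer that a whole cohort could be dosed on such a forecast, with the 30-fold margin to the dog data cut to about 24, 22 or 17-fold. Rule 4 prevents that. At 50% CV it refuses any cohort forecast above 2.68 µg.h/mL, below all three bands. The Cmax bands, which start at 0.356, 0.319 and 0.256 µg/mL, lie above 0.242 in the same way. At 30% CV the AUC gate is 3.36, and only part of the b = 1.5 band passes. These bands and margins apply at most to individual predictions under rule 5.

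**Conclusion.** The point holds in a narrow form. Before three dose levels, and only if population PK is not feasible, neither document gives a forecast rule for a more-than-proportional rise, and proportionality is the only fallback written down. At a 3-fold step the forecast is then low by a factor of 1.25 to 1.73. A dose set at the 10% gate would carry a true exceedance of about 21% to 45%. These figures rest on an assumed slope of 1.2 to 1.5 that persists over the next step, on lognormal exposure with the 50% CV stated for clearance, and on rule 4 being worked out from the proportional forecast.

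The separate fault in the fold-ratio rule follows from its algebra wherever the power relation holds.

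A reader might also take the 90 mg range as evidence of harm. It is not: its upper end, 7.09 µg.h/mL, would already be refused under a proportional forecast. It shows only that the gate can matter at dose 3. This is a cheap improvement of low to moderate priority.

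**What to change.** In Protocol 10.3.1 and SAP 7.1.3, replace the fold-ratio sentence with:

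> When two dose levels are available and population PK modelling is not feasible, the next exposure will be predicted from the observed log-log slope b = ln(exposure fold)/ln(dose fold), using geometric means, separately for AUC(0-24) and Cmax; the predicted exposure fold is (dose fold)^b. If b is below 1 and the next dose fold is larger than the previous one, the predicted fold will be no lower than the next dose fold multiplied by the previous ratio of exposure fold to dose fold.

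Keep the 3-fold cap and use this forecast in rules 4 and 5. If the Charter already contains such a rule, bring it into both documents.

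No forecast then falls below the current fallback. For b above 1, f^b exceeds f. For b below 1 and a next step no larger than the last, f^(b−1) is at least F1^(b−1). For a larger next step, the floor keeps the current value.

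The cost is one or two sentences per document and no new data. The two-dose slope is noisy. At an assumed 50% CV, with six active subjects per dose treated as independent, SE(b) = 0.472 × √(2/6)/ln(F1) = 0.15, 0.25 or 0.39 after a 6, 3 or 2-fold first step. If kinetics are truly proportional and b exceeds 1 by chance, a 3-fold forecast is too high on average by 3^(SE × √(2/π)) = 1.14, 1.24 or 1.41-fold. That is the safe direction, and the price is possibly one smaller step before the power model takes over.
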